5.1. Inclusion Criteria

Subjects are eligible to be included in the study only if they meet all of the following criteria:

- [1] are male or female between the ages of 18 and 65 years (inclusive) at the time of initial screening and are able and willing to provide written informed consent as a legal adult according to local regulations
- [2] female subjects of childbearing potential: test negative for pregnancy at screening and agree not to breastfeed from the start of screening until 2 weeks after the last dose of study drug
- [3] female subjects: agree to use a reliable method of birth control (eg, intrauterine contraceptive devices, hormonal contraceptives, or complete abstinence from sexual intercourse with men) from the start of screening until 28 days after the last dose of study drug or be classified as female subjects of nonchildbearing potential, defined as meeting at least 1 of the following criteria:
 - are postmenopausal with spontaneous amenorrhea for at least 12 months and have a follicle-stimulating hormone level >40 mIU/mL (>40 IU/L) at screening
 - have undergone bilateral tubal ligation, bilateral oophorectomy, and/or hysterectomy at least 6 weeks prior to screening
 - have another medical cause of female infertility that has been discussed with and accepted in writing by the sponsor

- [4] male subjects: agree to use a reliable method of birth control from the start of screening until 2 weeks after the last dose of study drug (eg, barrier contraceptives, such as latex condoms, or complete abstinence from sexual intercourse with women) or have undergone vasectomy at least 6 weeks prior to screening with documentation of sperm-free ejaculate
- [5] have a diagnosis of RA based on the 2010 ACR/European League against Rheumatism criteria (Aletaha et al. 2010) for at least 6 months prior to screening.
- [6] have at least 1 of the following:
- positive test results for rheumatoid factor or anti-citrullinated peptide antibodies (ACPA) at screening
- OR
- previous radiographs documenting bony erosions in hands or feet consistent with RA
- [7] have active RA, defined as meeting all of the following criteria at screening:
- Part A:** ≥ 3 swollen joints (based on 66-joint counts)
- Part B:**
- ≥ 6 swollen joints (based on 66-joint counts)
 - ≥ 6 tender joints (based on 68-joint counts)
 - high-sensitivity C-reactive protein (hsCRP) levels greater than the upper limit of normal (ULN) OR positive test results for ACPA
- [8] **Part B only:** have had inadequate response, loss of response, or intolerance to at least 1 synthetic or biologic DMARD treatment for RA, regardless of treatment duration
- [9] have venous access sufficient to allow blood sampling per protocol
- [10] are reliable, willing, and able to follow study procedures (in the opinion of the investigator) and will be available for the duration of the study

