 - history of serious opportunistic or chronic/recurring infection(s) within 6 months prior to screening (such as infections requiring IV antibiotics, hospitalization, or prolonged treatment) or deemed by the investigator to be immune compromised, such that participation in the study would pose an unacceptable risk to the subject
 - have a predisposed high risk of infection or risk of serious complications from infection, such as a history of infected joint or heart valve prosthesis (with prosthesis still in situ), an indwelling urinary catheter, etc.
- [23] have had lymphoma, leukemia, or any malignancy within the previous 5 years except for basal cell or squamous epithelial carcinomas of the skin that have been resected with no evidence of recurrence or metastatic disease
- [24] have a concomitant autoimmune or connective tissue disease at screening that is deemed active enough to interfere with the subject's safety or with evaluation of RA disease activity, in the opinion of the investigator

- [25] have a bleeding disorder, anti-phospholipid antibody syndrome or other hypercoagulable disorder, are on chronic anticoagulation therapy such as warfarin or heparin, or are on an antiplatelet agent such as clopidogrel or ticlopidine (a stable regimen of aspirin is permitted)
- [26] have a history of acute or chronic pancreatitis of any etiology, or severely uncontrolled hypertriglyceridemia, in the opinion of the investigator
- [27] have had any surgical procedure (except for minor surgery requiring only local or no anesthesia and without any complications or sequelae) within 12 weeks prior to screening or have any planned surgical procedure scheduled to occur during the study
- [28] have a history of clinically significant multiple or severe drug allergies or a history of severe posttreatment hypersensitivity reactions (including, but not limited to, erythema multiforme major, linear IgA dermatosis, toxic epidermal necrolysis, or exfoliative dermatitis)
- [29] have clinically significant or uncontrolled cardiovascular disease (eg, hypertension, angina, or congestive heart failure); endocrine disorder (eg, diabetes, thyroid dysfunction); or respiratory, hepatic, renal, gastrointestinal, hematologic, or neuropsychiatric disorder, including recent history of suicide attempt
- [30] have any other clinically significant condition, abnormality, or finding that may compromise the subject's safety or confound data analysis, according to investigator judgment

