6.2.2. Important Protocol Deviations

Important protocol deviations that potentially compromise the data integrity and subjects' safety will be summarized (by treatment group for all mITT subjects).

[Table JPDA.6.1](#) lists the categories, subcategories, and study specific terms of important protocol deviations, source of identification, and the method to identify each deviation.

Table JPDA.6.1. Description of Important Protocol Deviations

Category / Subcategory / Study specific	Source	Methods of Identification	Excluded from the Per Protocol Analysis
Category: Informed Consent			
Informed Consent Not Obtained/Missing/Late	Programmable (Clinical database)	If subject informed consent date is missing or after Visit 1 date	Yes
Category: Eligibility			
Subcategory: Inclusion/Exclusion			
Failed to meet the following eligibility criteria but was still enrolled into the study			
[1] Age ≥ 18 or ≤ 65 yrs	Programmable (Clinical database)	If year of ICD - Year of birth is < 18 years or > 65 years	Yes
[2] positive pregnancy test	Programmable (Clinical database)	If (positive serum pregnancy test at screening or urine pregnancy test at baseline) and subject has visit, Positive pregnancy test by central lab at screening or local lab UPT at baseline	Yes
[5] diagnosis of RA for at least 6 months prior to screening	Programmable (Clinical database)	If Visit 1 - RA diagnosis date is less than 180 days (6 months)	Yes
[6] either positive test results for RF or ACPA at screening OR Previous radiographs documenting bony erosions	Mixed [non-programmable (Monitoring) and Programmable (Clinical database)]	Should have documentation of previous radiographs of bony erosions in hands or feet. If RF and ACPA are negative and no documentation of previous radiographs of bony erosions in hands or feet.	Yes
[7] active RA	Programmable (Clinical database)	Part A: at least 3 swollen joints Part B: at least 6 swollen joints, 6 tender joints, hs-CRP $>$ ULN or positive test result for ACPA	Yes
[8] prior DMARD treatment (Part B)	Programmable (Clinical database)	At least 1 prior therapy is reported for Rheumatoid Arthritis	Yes
[11] prior enrollment in study	Non-programmable (Monitoring)	Any documentation indicate same subjects enroll to Part A and B.	Yes

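### Inclusion [2] asks only women of childbearing potential to agree not to breastfeed, so a lactating woman classed as nonchildbearing under [3] is not covered

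*Protocol*

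**What the plan says.** Protocol 5.1, inclusion [2], puts two requirements behind one population label: "female subjects of childbearing potential: test negative for pregnancy at screening and agree not to breastfeed". The agreement lasts as follows: "agree not to breastfeed from the start of screening until 2 weeks after the last dose of study drug".

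Inclusion [3] addresses all female subjects, but only on contraception. A woman must use reliable birth control "or be classified as female subjects of nonchildbearing potential, defined as meeting at least 1 of the following criteria". One of the listed routes is to "have undergone bilateral tubal ligation, bilateral oophorectomy, and/or hysterectomy at least 6 weeks prior to screening". The others are a postmenopausal route and another medical cause of infertility that the sponsor accepts in writing.

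Two exclusions in Protocol 5.2 bear on the same woman:

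- [27], whose period is counted back from the screening visit, excludes those who "have had any surgical procedure (except for minor surgery requiring only local or no anesthesia and without any complications or sequelae) within 12 weeks prior".
- [30] excludes those who "have any other clinically significant condition, abnormality, or finding that may compromise the subject's safety or confound data analysis, according to investigator judgment".

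In SAP 6.2.2, Table JPDA.6.1, the programmed deviation check for [2] is "If (positive serum pregnancy test at screening or urine pregnancy test at baseline) and subject has visit".

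**The concern.** Childbearing potential decides whether a pregnancy test is informative. It does not decide whether a woman can be producing milk. Because one label carries both requirements, the breastfeeding restriction reaches only women who could become pregnant. A woman who has been sterilised but is nursing falls outside it.

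The protocol does not state why it restricts breastfeeding. The natural inference is that the clause is meant to spare a nursing infant exposure to the study drug. Protocol 2.1 describes LY3337641 as an irreversible BTK inhibitor and notes that human BTK loss of function lowers B-cell and immunoglobulin levels. Protocol 4.5 reports gastrointestinal injury as the main animal toxicity, with pancreatic and immune effects also seen. The sponsor thought a breastfeeding restriction necessary, and nothing in the rationale for it depends on the mother's fertility. The person at risk is an infant, who cannot consent.

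**Working it through.** This is mainly a reading of the criteria against each other; the only arithmetic is the length of the window.

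**1. Scope of [2].** The population label stands before the colon and both requirements follow it, joined by a conjunction. No separate population is given for the breastfeeding agreement, so it applies to women of childbearing potential only.

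**2. Who leaves that scope under [3] and could still be lactating.**

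| Route to nonchildbearing status | Compatible with lactation? |
|---|---|
| Postmenopausal: 12 months of amenorrhea and FSH above 40 mIU/mL | Adds little in practice |
| Bilateral tubal ligation or hysterectomy, at least 6 weeks before screening | Yes |
| Other infertility accepted in writing by the sponsor | Possible, but with a sponsor check |

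**3. Timing.** Take a bilateral tubal ligation done at delivery more than 12 weeks before screening. It is more than 6 weeks old, so [3] classes her as nonchildbearing. It is outside the 12-week window, so [27] does not exclude her. [27] therefore narrows the gap but leaves it open for any woman still nursing after that point.

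**4. Does anything else close it?** Inclusion [1] and [3] to [10] and exclusion [11] to [36] were read for breastfeeding or lactation; none names either. Exclusion [30] is discretionary and turns on the subject's own safety or on confounding, not on an infant. Inclusion [10] concerns willingness to follow study procedures, and for this woman not breastfeeding is not one of them. The Schedule of Activities (Protocol Appendix 2) has no lactation item. The SAP check for [2] reads pregnancy results only, so it would not reveal her enrolment.

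**5. Length of the missing agreement.** Inputs are from Protocol Appendix 2 and inclusion [2], using nominal visit days.

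- Part B: screening up to 28 days + dosing 84 days (Study Days 1 to 85) + 14 days after the last dose = 126 days; 126 / 7 = 18 weeks. Dosing alone is 84 / 7 = 12 weeks.
- Part A: 28 + 28 (Study Days 1 to 29) + 14 = 70 days; 70 / 7 = 10 weeks. Dosing alone is 4 weeks.

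These are upper figures for one woman. Randomization is 1:1:1:1 with one placebo arm, so three of four such women would receive active drug. Nothing is projected to the long-term extension, whose addendum was not available.

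**The case against.** The strongest reply is that the group is close to empty. A woman must be breastfeeding, be sterilised early enough to clear [3] and [27] (or have a cause of infertility the sponsor has accepted), and have RA diagnosed at least 6 months before screening. In Part B she must also have at least 6 swollen and 6 tender joints and an inadequate response, loss of response or intolerance to a DMARD. No endpoint, power or error rate is touched. This is right, and it limits the size of the concern. It does not alter what the criterion says.

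Second, other safeguards may exist. A complete medical history is taken at screening and records are reviewed before randomization (Protocol 5), so a recent delivery would probably come to light. The consent form, not available here, may tell all women not to breastfeed. These may well work in practice, but the listed criteria give the investigator no stated ground for exclusion beyond judgment, and an instruction in the consent form would be a reason to align the criterion with it.

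Third, exposure may be slight: Protocol 2.1 gives a plasma half-life of 4.6 to 6.6 hours, and there are no milk-transfer data. This stands, and it is why the point is precautionary.

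Fourth, the SAP check would also miss a breastfeeding woman of childbearing potential, so it is not part of the scope error. Agreed; it shows only that the deviation listing offers no backstop.

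**Conclusion.** The concern holds. Applied exactly as written, Protocol 5.1 admits a lactating woman with a past tubal ligation or hysterectomy without the agreement it requires of other women, and no other listed criterion names breastfeeding. This is a stated rule with the wrong scope rather than a missing detail.

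Confidence in the reading of the criteria is high. The practical size is an unknown, very small and possibly zero number of women, each with up to about 18 weeks uncovered in Part B. The conclusion is limited to the listed eligibility criteria. It assumes that the clause is there to protect a nursing infant, and it makes no claim about how much drug reaches milk. The change is worth making because the risk falls on a third party and the correction costs almost nothing.

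**What to change.** Split inclusion [2] into two criteria, each with its own population:

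- **[2a]** Female subjects of childbearing potential: a negative pregnancy test at screening.
- **[2b]** All female subjects: "agree not to breastfeed from the start of screening until 2 weeks after the last dose of study drug".

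This keeps pregnancy testing limited to women of childbearing potential and extends only the breastfeeding agreement. The cost is one line of protocol wording, with matching consent wording if it is not already there. No test or visit is added, and the effect on recruitment is close to nil. The split does not by itself make the SAP deviation check detect breastfeeding.

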5.2. Exclusion Criteria

Subjects will be excluded from study enrollment if they meet any of the following criteria:

- [11] have previously completed or withdrawn from any part of this study (does not apply to subjects who are allowed to rescreen prior to randomization)
- [12] have received any of the following synthetic immunosuppressive therapies under the defined conditions:
- methotrexate (MTX), hydroxychloroquine, sulfasalazine, or leflunomide at an UNSTABLE PRESCRIBED DOSE (defined as a change in prescription) within 28 days prior to baseline or planned dose change (including initiation or

discontinuation) during the study. The following therapies are permitted during the study:

- parenteral MTX up to 20 mg/week OR oral MTX up to 25 mg/week (subjects on MTX should receive supplementation with folic acid according to local standard of care)
- hydroxychloroquine up to 400 mg/day
- oral sulfasalazine up to 3000 mg/day
- leflunomide up to 20 mg/day
- concomitant treatment with MTX plus leflunomide within 28 days prior to baseline or planned concomitant treatment with both during the study
- gold salts, kinase inhibitors (such as tofacitinib), cyclophosphamide, mycophenolic acid, azathioprine, cyclosporine, sirolimus, or tacrolimus within 28 days prior to screening or planned treatment during the study
- **Part B only:** any prior treatment with a product directly targeting BTK (marketed or investigational)

[13] have received any of the following biologic immunosuppressive therapies under the defined conditions or plan any such treatments during the study (other biologic agents may be allowed after discussion with the sponsor and upon agreement in writing):

- etanercept, adalimumab, or anakinra within 14 days prior to baseline
- infliximab, certolizumab pegol, golimumab, abatacept, or tocilizumab within 4 weeks prior to baseline
- belimumab, natalizumab, or vedolizumab within 6 months prior to baseline
- **Part A only:** B-cell-depleting agents (such as rituximab) or other cell-depleting biologics (eg, anti-CD3 antibody) within 12 months prior to screening
- **Part B only:** B-cell-depleting agents (such as rituximab) or other cell-depleting biologics (eg, anti-CD3 antibody) at any time prior to screening

[14] have received any of the following other types of therapies under the defined conditions:

- parenteral corticosteroids within 28 days prior to baseline or planned treatment during the study. (A single intra-articular corticosteroid injection is permitted within 28 days prior to baseline if no more than 40 mg triamcinolone [or equivalent] is administered and no further injections are planned during the study. The treated joint should be excluded from any joint-specific evaluations during the study.)
- prescription for oral prednisone (or equivalent) >10 mg/day or UNSTABLE PRESCRIBED DOSE within 28 days prior to baseline
- a chronic narcotic drug at an UNSTABLE PRESCRIBED DOSE within 28 days prior to baseline or planned increase/new prescription during the study
- gemfibrozil (a strong cytochrome P450 2C8 inhibitor) or alfentanil, dihydroergotamine, dofetilide, ergotamine, fentanyl, pimozone, or quinidine

(sensitive narrow therapeutic index cytochrome P450 3A substrates) within 28 days prior to baseline or planned treatment during the study

[15] have any clinically significant hematological or chemistry abnormalities at screening, including

- hemoglobin level <8.5 g/dL (<85 g/L)
- total platelet count <100 × 10⁹/L (<100 × 10³/μL or <100 Gi/L)
- total white blood cell count <3.0 × 10⁹/L (<3.0 × 10³/μL or <3.0 Gi/L)
- aspartate aminotransferase (AST) level >2.5 × ULN
- alanine aminotransferase (ALT) level >2.5 × ULN
- creatinine level ≥1.5 mg/dL (≥129 μmol/L)
- amylase >1.5 x ULN
- lipase >1.5 x ULN

A single repeat analysis is allowed according to investigator judgment prior to making a final determination of eligibility. The repeat laboratory test does not require a re-consent because the result does not constitute a screening failure until the clinically significant, out-of-range value is confirmed.

[16] have known hypogammaglobulinemia or a screening serum IgG level <565 mg/dL (<5.65 g/L)

A single repeat analysis is allowed according to investigator judgment prior to making a final determination of eligibility. The repeat laboratory test does not require a re-consent because the result does not constitute a screening failure until the clinically significant out-of-range value is confirmed.

[17] have evidence of or test positive for hepatitis C virus (HCV) at screening (defined as a positive test result for hepatitis C antibody [anti-HCVAb] plus a positive confirmatory test result for HCV [eg, HCV RNA])

Subjects whose results are anti-HCVAb positive and HCV RNA negative can be enrolled in the study, according to investigator judgment.

[18] have evidence of or test positive for hepatitis B virus (HBV) at screening, defined as (1) testing positive for hepatitis B surface antigen OR (2) testing positive for anti-hepatitis B core antibody (HBcAb) AND positive for HBV DNA

Subjects whose results are HBcAb positive and HBV DNA negative may be enrolled in the study, according to investigator judgment. Subjects whose results are HBcAb positive and HBV DNA negative at screening will be monitored for HBV during the study as detailed in Section 8.4.7.1.

[19] have evidence of or test positive for human immunodeficiency virus at screening

[20] have symptomatic herpes zoster within 6 months prior to screening that constitutes a clinically significant risk to the subject (according to investigator judgment)

- [21] have active tuberculosis (TB) determined on the basis of a positive medical history, physical examination, or chest radiography (per local standard of care) or have exclusionary TB test results, which include either of the following:
- a positive tuberculin skin test (TST) result (defined as a skin induration >5 mm at 48 to 72 hours after the test date, regardless of Bacillus Calmette-Guérin vaccination history) or
 - a positive (or persistently indeterminate/invalid/borderline) interferon γ release test (eg, QuantiFERON[®]-TB Gold or T-Spot[®].TB)

The choice to perform either a TST or an interferon γ release test will be made by the investigator according to local licensing and standard of care. If the QuantiFERON-TB Gold is indeterminate or the T-Spot.TB is invalid or borderline, one retest is allowed according to investigator judgment. If the repeat test is also indeterminate, the subject will be excluded. The interferon γ release test can be used only in countries where it is licensed, and the use of this test is dependent on previous treatment(s).

Subjects with known latent TB should not undergo a TST or interferon γ release test and must have documentation of receiving at least 4 weeks of appropriate, ongoing latent TB therapy, according to local standard of care, prior to screening. Such patients must continue/complete appropriate latent TB therapy during the course of the study in order to remain eligible.

- [22] are at high risk of infection or have recent evidence of clinically significant infection, based on findings that include the following:
- fever of 100.5°F (38°C) or above at screening or baseline that is not due to the underlying autoimmune disease (eg, RA)
 - history of serious opportunistic or chronic/recurring infection(s) within 6 months prior to screening (such as infections requiring IV antibiotics, hospitalization, or prolonged treatment) or deemed by the investigator to be immune compromised, such that participation in the study would pose an unacceptable risk to the subject
 - have a predisposed high risk of infection or risk of serious complications from infection, such as a history of infected joint or heart valve prosthesis (with prosthesis still in situ), an indwelling urinary catheter, etc.
- [23] have had lymphoma, leukemia, or any malignancy within the previous 5 years except for basal cell or squamous epithelial carcinomas of the skin that have been resected with no evidence of recurrence or metastatic disease
- [24] have a concomitant autoimmune or connective tissue disease at screening that is deemed active enough to interfere with the subject's safety or with evaluation of RA disease activity, in the opinion of the investigator

- [25] have a bleeding disorder, anti-phospholipid antibody syndrome or other hypercoagulable disorder, are on chronic anticoagulation therapy such as warfarin or heparin, or are on an antiplatelet agent such as clopidogrel or ticlopidine (a stable regimen of aspirin is permitted)
- [26] have a history of acute or chronic pancreatitis of any etiology, or severely uncontrolled hypertriglyceridemia, in the opinion of the investigator
- [27] have had any surgical procedure (except for minor surgery requiring only local or no anesthesia and without any complications or sequelae) within 12 weeks prior to screening or have any planned surgical procedure scheduled to occur during the study
- [28] have a history of clinically significant multiple or severe drug allergies or a history of severe posttreatment hypersensitivity reactions (including, but not limited to, erythema multiforme major, linear IgA dermatosis, toxic epidermal necrolysis, or exfoliative dermatitis)
- [29] have clinically significant or uncontrolled cardiovascular disease (eg, hypertension, angina, or congestive heart failure); endocrine disorder (eg, diabetes, thyroid dysfunction); or respiratory, hepatic, renal, gastrointestinal, hematologic, or neuropsychiatric disorder, including recent history of suicide attempt
- [30] have any other clinically significant condition, abnormality, or finding that may compromise the subject's safety or confound data analysis, according to investigator judgment
- [31] have received a live (attenuated) vaccine within 28 days prior to baseline or plan to receive one during the study
- [32] are currently enrolled in any other clinical trial involving an investigational product (IP) or any other type of medical research judged not to be scientifically or medically compatible with this study or have received any of the following IPs under the defined conditions:
- any nonbiologic IP within 5 half-lives prior to baseline
 - any leukocyte-depleting agent (eg, anti-CD22 or anti-CD3) at any time
 - any non-cell depleting biologic IP within 90 days or 5 drug half-lives (whichever is longer) prior to screening
- [33] have donated more than 500 mL of blood within 28 days of screening or plan to donate blood during the study
- [34] have a history of significant alcohol or drug abuse or are currently a heavy smoker, in the opinion of the investigator
- [35] are investigator site personnel directly affiliated with this study and/or their immediate families (defined as a spouse, parent, child, or sibling, whether biological or legally adopted)

[36] are Lilly employees or are employees of third-party organizations involved in the study

